## 4.9. SAMPLE SIZE

Feasibility RCT: We aim to randomise 105 men, 35 to each arm, in line with recent recommendations for pilot trials as sufficient to estimate key parameters for a full trial. We will conduct 18-30 face to face or telephone interviews (6-8 men from each trial group) recruited throughout the trial. This sample size is based on previous experience of conducting feasibility studies like this. A sampling frame will ensure diversity for socio-demographic and personal weight loss histories.

Mixed methods process evaluation: All men (n=105) who attend the 12 month assessment will be asked an open question for any suggestions for improving the study. Men who do not attend will be sent a final "thank you" letter informing them of how they can access the findings, and will be invited to provide feedback. Based on previous research experience of applying qualitative research in feasibility RCTs, 18-30 qualitative semi-structured interviews, with a diverse and information rich sample (6-10 from each trial group) are likely to be required to reach data saturation for key themes and for no new thematic issues to arise in interviews. However, some flexibility in the precise sample size is required, as it is impossible to predict important research questions that might arise in a complex intervention study like this. The PhD student will also conduct an additional 18-30 semi-structured interviews to investigate variation in engagement of men and to find out about their experiences after the intervention has finished.

## 4.10. THE ANALYSIS PLAN FOR THIS STUDY

Given the feasibility nature of the study, the data reported will mainly be descriptive. Summaries of quantitative outcome measures (all time points) will be tabulated by intervention group, including means and standard deviations for continuous variables e.g. weight loss (or medians and interquartile ranges if data are skewed), and proportions for any dichotomous or categorical data. The proportion of individuals contacted who were recruited and the proportion retained in the study at various time-points by group will be determined. Unadjusted mean differences and risk ratios will be calculated for 12 month outcomes to determine evidence of

potential effect of the interventions to test progression criteria, but no further estimates of effect size will be modelled. Completion rates will be reported so that the feasibility of each outcome measure can be assessed. A sample size calculation for a full trial will be performed, incorporating the standard deviation and response rates for the primary outcome. The proportions of participants who ask to stop the texts, withdraw from the study and attend the 3 month assessments will be compared for the original and alternative text messages.

Health Economics: The feasibility of measuring cost and outcomes for the cost-effectiveness analysis in the full trial will be explored. In a future full trial, cost-effectiveness of the interventions will be measured as a cost per Quality Adjusted Life Year (QALY) from an NHS perspective. The resources associated with the interventions will be abstracted from study forms. Other NHS resource use will be collected from participant questionnaires. Resource use estimates will be combined with unit costs obtained from standard sources or study specific estimates. QALYs will be derived from the responses to the EQ-5D. The incremental cost effectiveness ratio (ICER) will be estimated by dividing the difference in mean total costs between the intervention and control group by the difference in QALYs. Bootstrapping will be used to estimate variability in the ICER. A Value of Information analysis will be done to give an indication of the optimal sample size of a future trial.

**Mixed method and qualitative data analysis:** Anonymised transcripts of interviews, recruitment and attrition data, trial group, participant characteristics and outcomes will be entered into NVivo10 or similar software for analysis guided by a Framework approach. The data collection, data analysis, reflection and refinement on the research questions, modification of the sampling strategy, topic guides and the coding frame will be an iterative process throughout the study. Notes from researchers' reflexive diaries kept during recruitment and assessment appointments and any free text responses from the on-line exit survey may also be entered onto NVivo and included in the analysis. Analysis will be driven by the key feasibility and acceptability research questions and objectives and any uncertainties emerging as the study progresses. Two researchers will independently develop a coding frame (agreed through team discussion) and identify key themes after reading a diverse sample of interviews. Thematic analysis will involve summarising mixed method data and constructing charts to compare and contrast data across the study groups and men with different characteristics. When reporting qualitative data findings, any quotations or data will be anonymised so that participants cannot be recognised.

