**iv) Enrolment.** If men have expressed an interest in joining the study, they will be invited to attend an appointment at a convenient venue and time with a researcher. Collaboration with PPI and local stakeholders, together with findings from a survey of 1045 obese men has identified acceptable local community venues (e.g. GP surgeries, pharmacies, community centres, schools). GP surgeries were the most popular choice of venue for assessments.

Men will be able to attend with a relative or friend. At the enrolment appointment the researcher will ensure that the man has a copy of the full study information leaflet, will discuss this, answer any questions and gain written informed consent. Confidentiality of data will be explained and we will request that men do not discuss which group they are allocated to with

other men participating in the study or to talk about the study on social media. This is to reduce any contamination, which could interfere with the study outcomes in this individual RCT. Participants will be informed that they can choose whether to participate or not and they can withdraw from the study at any point if they wish, without any personal consequences.

- iv) Baseline data collection: Researchers will document the number needed to approach for an attendance at baseline assessment (N= number approached/for one attendance at baseline assessment); and number needed to approach for a successful recruitment (N= number approached/for one randomised). To assess reach, we will document the number of men personally invited (GP recruits), approached in the community and indicating initial interest, attending enrolment appointment, consenting to randomisation, self-reported eligibility and verified eligibility (weight and waist circumference measured). Any reasons given for dropping out at any stage will be documented. The Health Informatics Centre (HIC) at the University of Dundee has participant tracker software (safe haven). Researchers will collect baseline data and assessments (Table 2) following the procedures described in 4.6. The researcher will request independent randomisation by Tayside Clinical Trials Unit (TCTU) using a secure remote web-based system (telephone backup). TCTU will stratify by the two recruitment methods: GP and community. After group allocation, all men will be given a pedometer and a unique ID which will allow them to access the study webpage appropriate for their allocated group.

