## Secondary outcomes for this study:

Process data: differential recruitment, intervention engagement and retention by socioeconomic status, recruitment strategy (GP practice or community venues) and geographical area (deprivation index). Impact on quality of motivation (intrinsic and extrinsic), satisfaction with weight loss. Qualitative experiences, including acceptability of the incentive, the impact on social networks and families, need for additional support, unintended consequences e.g. incentive gaming, sustainability. Usual practice while on the waiting list will be described, and compared with each intervention group.

**Future full RCT- proposed primary outcome is:** mean difference in weight loss (absolute and percentage) between groups at 12 months.

**Future full RCT - proposed secondary outcomes** (may change depending on the findings of this study): waist circumference, QALYs, costs, cost-effectiveness. PhD studentship is investigating the feasibility of follow-up until 24 months and data linkage to routinely collected health outcomes, e.g. hospital admissions, obesity related diagnoses such as diabetes, cancers, heart disease, high blood pressure.

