## 4.6. ASSESSMENT AND FOLLOW UP

Weight outcomes will be collected at baseline, 3, 6 and 12 months (standard time points in weight loss studies); these were acceptable in our survey of obese men and with our PPI group. Assessment at 3 months, will allow early identification (and rectification) of any problems with the trial design.

Assessments use validated tools where available and follow quality standards for measurement procedures. These are summarised in Table 1. More detail is provided in section 4.7

Table 1: Assessment schedule of essential and desirable variables according to male obesity programmes checklist from the Men's Health Forum (MHF)

Essential variables	0	3	6	12
Socio-demographics, co-morbidities, disability, ethnicity	✓			
Anthropometry (height, weight, BMI, waist circumference)	✓	✓	✓	✓
Mixed methods process/acceptability data	✓	✓	✓	✓
Lifestyle behaviours and activities (diet, PA, smoking, alcohol)	✓		✓	✓
Health Economic Outcomes: EQ-5D, NHS health care use	✓		✓	✓
Theory-based mediators	√	√	√	✓
Wellbeing	√			✓

Mixed methods data collection: will assess the acceptability and feasibility of different venues, recruitment strategies, randomisation, retention and outcome collection. We will collect i) numerical data on attendance at appointments, ii) monitor intervention engagement through response rates to SMS, iii) researchers will informally ask men how they are getting on with being in the study and collect field notes of participant experiences when collecting outcome data at 3 months, 6 months and 12 months. A purposive sample of diverse and information rich men will be invited to volunteer for longer semi-structured qualitative interviews (6-10 from each trial group) at 12 month assessments or at a separate appointment (participant choice: face to face, telephone, Skype). The qualitative interview sampling frame and topic guide will be modified iteratively according to the emerging analysis. Perceptions on the original texts and the alternative texts will be explored by showing men a sample of the texts that they have not received. Think-aloud techniques will be used to understand preferences for style and content. The researchers will complete a reflexive diary of participant discussions, which will contribute to the mixed methods data collection and analysis.

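### Section 4.10 limits the 12-month between-arm comparisons to unadjusted differences, giving up precision for waist, EQ-5D and wellbeing that baseline data already collected would supply

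*Protocol*

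**What the plan says.** Section 4.10 opens by setting a modest purpose: "Given the feasibility nature of the study, the data reported will mainly be descriptive". For comparisons between arms it states "Unadjusted mean differences and risk ratios will be calculated for 12 month outcomes". It gives their use as evidence of "potential effect of the interventions to test progression criteria", and closes the matter with "but no further estimates of effect size will be modelled". The same section carries the results into planning: "A sample size calculation for a full trial will be performed, incorporating the standard deviation and response rates for the primary outcome".

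The data needed for adjustment are in the plan:
- Section 4.6 states "Weight outcomes will be collected at baseline, 3, 6 and 12 months". Its assessment schedule ticks anthropometry (including waist), EQ-5D and wellbeing at both month 0 and month 12.
- Section 4.2, in the baseline data collection item, states "TCTU will stratify by the two recruitment methods: GP and community".

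For the future trial, section 4.5 proposes as primary outcome the "mean difference in weight loss (absolute and percentage) between groups at 12 months". Section 4.11 mentions generalised linear models as an example of the approach for that trial.

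**The concern.** This is a choice the protocol makes, not a detail left to a statistical analysis plan. Unadjusted estimates are prescribed and further modelling is excluded, so an analysis plan could not add a baseline-adjusted estimate without departing from the protocol.

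At this sample size, chance differences between arms at baseline are common. An unadjusted comparison of 12-month values carries most of such a difference into the estimate when the outcome is strongly correlated over time. A comparison of changes over-corrects when the correlation is low. Adjusting for the baseline value avoids both.

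The between-arm estimates can inform the steering committee's judgement on a two- or three-arm trial, and the SD goes into the full-trial sample size. A noisier estimate is therefore a real, if limited, cost.

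**Working it through.** **The plan's own figure.** Section 4.9 gives 35 men in each of three arms: 3 × 35 = 105, which agrees. The size rests on a cited recommendation for pilot trials. No effect size, SD, alpha or power is stated, so there is no power calculation to reproduce.

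**Number measured.** Progression criterion 3 in section 3 asks for 12-month outcomes on at least 72% per group: 0.72 × 35 = 25.2, so 26 men per arm at the floor.

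**Assumed inputs.** The protocol gives no baseline-to-12-month correlation *r* and no SD. I take *r* = 0.5 to 0.7 for waist, EQ-5D and wellbeing, and 0.90 to 0.95 for weight. Results are in units of a common outcome SD.

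**Formulas**, with *n* per arm:
- 12-month values: SE = √(2/n)
- change from baseline: SE = √(2/n) × √(2(1 − r))
- baseline-adjusted (ANCOVA): SE = √(2/n) × √(1 − r²) × √(1 + 1/(2n − 4)), the last factor being the small-sample cost of one covariate

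**Results at n = 26**, where √(2/26) = 0.277:

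| r | SE, values | SE, change | SE, adjusted | Adjusted ÷ values | Adjusted ÷ change |
|---|---|---|---|---|---|
| 0.5 | 0.277 | 0.277 | 0.243 | 0.875 | 0.875 |
| 0.7 | 0.277 | 0.215 | 0.200 | 0.722 | 0.932 |
| 0.9 | 0.277 | 0.124 | 0.122 | 0.440 | 0.985 |
| 0.95 | 0.277 | 0.088 | 0.088 | 0.315 | 0.998 |

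A simulation of 20,000 trials at n = 26 gave the same standard errors to within 0.002. The ratios at n = 35 are nearly identical.

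- *Waist, EQ-5D, wellbeing* (r = 0.5 to 0.7): adjustment lowers the SE by about 12–28% against 12-month values, or about 7–12% against changes. Section 4.10 does not say which would be compared.
- *Weight loss* (r = 0.90 to 0.95): it is a change from baseline, so the last column applies. The SE falls by about 0.2–1.5%.

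**Chance imbalance.** The between-arm difference in a baseline mean has SD √(2/n): 0.277 at n = 26 and 0.239 at n = 35. The chance that it exceeds 0.25 SD in a given comparison is about 37% and 30% respectively. An imbalance of 0.25 SD shifts a comparison of values by 0.25 × r, and a comparison of changes by 0.25 × (r − 1):

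| r | Shift, values | Shift, change |
|---|---|---|
| 0.5 | 0.125 | −0.125 |
| 0.7 | 0.175 | −0.075 |
| 0.9 | 0.225 | −0.025 |
| 0.95 | 0.2375 | −0.0125 |

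**Stratum.** If GP and community men differ by an assumed d = 0.2 to 0.5 SD, with equal strata, the stratum explains (d²/4) ÷ (1 + d²/4) of the outcome variance: 1% to 6%. The gain is small.

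**Weight in kilograms, for scale.** Assume SD 15–20 kg, r = 0.90 to 0.95, 26 per arm and a t multiplier of 2.01. The 95% half-width runs from 2.01 × 0.277 × 15 × √0.10 = 2.6 kg to 2.01 × 0.277 × 20 × √0.20 = 5.0 kg for unadjusted change. For the adjusted difference it is about 2.6 to 4.9 kg. The two are practically the same.

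**SD for the full trial.** The ratio of adjusted residual variance to change-score variance is (1 + r)/2, which is 0.95 to 0.975 at r = 0.90 to 0.95. For weight loss the residual variance is thus 2.5–5% smaller than the raw one.

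**The case against.** The strongest reply is that this is a deliberate and defensible choice. The study is a feasibility trial, reporting is mainly descriptive, no hypothesis test is planned, and modelling is deferred to the full trial. Unadjusted randomised differences are unbiased over randomisation. No SD or correlation is given, so the size of the loss cannot be read from the protocol. Waist, EQ-5D and wellbeing carry no decision threshold here. All of this stands, and it limits the point to efficiency. It does not make the noisier estimate preferable when a better one needs no further data.

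A reader might infer more, in four ways that the document does not support:
- *That the weight comparison is swamped by baseline noise.* Comparing raw body weight at 12 months would give half-widths of about 8 to 11 kg under the assumptions above (2.01 × 0.277 × 15 or 20). But sections 1b, 3, 4.5 and 4.10 all express the outcome as weight loss, which already removes most of the baseline difference.
- *That the go/no-go decision is compromised.* The only numerical weight criterion is a mean loss of at least 3% of baseline weight within an intervention group. Between-arm imbalance does not affect whether it is met.
- *That the full trial would be sized on the wrong variance.* For weight loss the discrepancy is 2.5–5% of variance, and it errs towards a larger trial. Section 4.11 gives its models as an example and names no covariates, so it does not contradict 4.10.
- *That every 12-month outcome could be adjusted.* Satisfaction with the intervention and counts of messages exchanged, for instance, have no baseline value.

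One consideration points the other way. Up to 28% may be missing at 12 months, and attendance incentives and interim contact differ by arm, so imbalance among completers need not be purely chance. Adjustment would help only where dropout depends on the measured baseline.

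**Conclusion.** The point holds as one of precision, not validity. Section 4.10 excludes an estimate that is at least as precise, apart from a negligible small-sample cost, and that removes the effect of chance imbalance in the measured baseline. The benefit is moderate for waist, EQ-5D and wellbeing: an SE lower by about 12–28% for values or 7–12% for changes, at assumed correlations of 0.5 to 0.7 and 26 men per arm. It is slight for weight loss (0.2–1.5% at assumed correlations of 0.90 to 0.95) and small for the stratum. The 3% progression criterion is unaffected. The gain for full-trial planning is an SD that matches whichever model that trial adopts. All magnitudes rest on assumed correlations; that the protocol restricts the analysis in this way does not.

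**What to change.** Amend the sentence in section 4.10 so that, beside the unadjusted figures, it provides mean differences with 95% confidence intervals from a linear model adjusted for the baseline value of the outcome (where one is measured) and for the recruitment-route stratum. Reword the exclusion of further modelling to allow this. State for each continuous outcome whether the unadjusted figure compares 12-month values or changes. Report the residual SD and the baseline-to-12-month correlation alongside the raw SD, so that the full-trial calculation can use the variance belonging to its planned analysis.

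The cost is a small change to one passage of the protocol and a little more analysis. Nothing further has to be collected, and the descriptive reporting already planned stays as it is.

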## THE STUDY HAS TWO PARTS:

PHASE 1. Is in progress and is setting up the feasibility trial. Phase 1 has approval from the University of Stirling Research Ethics Committee.

PHASE 2. We will study whether it is acceptable and possible to randomise obese men (like tossing a coin) to three groups: texts only; texts and incentive; or to a 'control group' who wait a year and then get the texts for 3 months. We will assess the feasibility of recruiting 105 obese men from two regions of Scotland. Half of the men will get an invitation letter from their GP. The other half will be approached in the community, given information about the study and invited to take part. Men can take part if their trouser waist is 40 inches and more or their Body Mass Index is 30 or higher. We want to find out how long it takes to find 105 obese men who want to take part, how many come back to suitable venues at 3, 6 and 12 months to get weighed and answer questions about their quality of life, lifestyle and motivation. We will try to include men from all walks of life, so we will ask questions at the start like their age, address, who they live with, or if they have any illnesses like diabetes. At the end we will ask men about their experiences and men from the control group will receive texts for 3 months if they wish. Control group texts will be developed based on the feedback and qualitative interview data received from the men in the two intervention groups at 3 months. In order to improve the acceptability of the texts to more men, these texts will be a different style from the original narrative texts. Drop-outs from the control group at 12 months will be replaced through recruiting further men until we have a sample of at least 30 men receiving the alternative texts. We will interview approximately 18-30 men in more detail about their experiences of weight loss and of being in the study. We will follow up all men from the alternative text group for 3 months, seek their feedback on the texts and interview 10-16 men in more depth about their experience. A PhD student will find out if it is possible to follow up the men for another year, and ask them questions on whether it is acceptable and possible to link the study findings to their health records.

Protocol, Game of Stones. V3, 14/02/2018

THE STUDY WILL TELL US if our approach is acceptable, possible to deliver and if it could help men to lose weight. If it is, then we will do a larger study.

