## Main research questions:

- 1. Are adapted narrative SMS interventions with embedded BCTs, with or without endowment incentives, acceptable and feasible to deliver in a RCT?
- 2. How can intervention components and outcome measurement procedures be optimised to increase reach, engagement and follow-up of obese men?
- 3. Are alternative SMS based on mixed method data analysis more acceptable and likely to improve trial retention at 3 months than the existing text message intervention?
- 4. Are progression criteria met for a full RCT for one or both interventions?
- 5. What are the likely recruitment and attrition rates?
- 6. What would be the sample size for a full trial of weight loss outcomes at 12 months?
- 7. How do the two interventions (SMS with and without endowment incentives) compare for health equalities, reach, engagement and retention?
- 8. Is data-linkage to long-term health and resource outcomes feasible? (Phases 1 and 2)

Main research question for a future full trial: Is a narrative SMS intervention with embedded BCTs, with or without an endowment incentive, effective and cost-effective in supporting weight loss and weight loss maintenance at 12 months in obese men compared to a waiting list control?

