The front page of the study website will be accessible to all participants. It includes essential information about the trial and links to existing on-line resources e.g. The NHS choices website: http://www.nhs.uk/LiveWell/Loseweight/Pages/Loseweighthome.aspx; and ManvFat: https://manvfat.com/;

The SMS only group web page will have a brief biography and images of the fictional characters featured in the narrative SMS and information specific to this trial arm. There will be also be a link for self-monitoring weight, waist circumference and pedometer steps. Our PPI work to date suggests practical and affordable measurement aids such as notches on belts, a piece of string with felt pen mark, and/or a tape measure.

The SMS with incentives group web page will have access to the same information as the SMS only group. It will also have an additional page about the financial incentives and progress towards weight loss targets.

The SMS waiting list group (control) will only have access to this front page until they have provided outcome data at 12 months. They will receive alternative SMS for 3 months and, similar to the original intervention groups will receive weight loss targets for 3, 6 and 12 months, get access to the webpage information sources and the self-monitoring tools and a pedometer.

WHAT-Procedures: All participants will receive automatic SMS according to the algorithm and SMS library. Men will be encouraged to set ambitious weight loss targets to start with of: 5% of body weight lost at 3 months, 10% at 6 months and 10% at 12 months after the start of the study. These will be personalised and identical to those in the SMS with incentive group. At the 3, 6 and 12 month weighing appointments, men will have the choice of continuing with these weight loss targets of 5%, 10% and 10% or setting lower targets of 5% of body weight at 6 months and 5% at 12 months.

WHO PROVIDES, HOW AND WHERE: The SMS will be delivered by HIC using existing tried and tested automated technology linked to Tayside Clinical Trials Unit currently used in other RCTs. Men will require a standard mobile phone (any type) to maximise reach.

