## **CONTROL GROUP**

Waiting list for SMS intervention: At the 12 month outcome assessment men will be offered an alternative SMS intervention for 3 months, based on the feedback received from intervention men at 3 months and qualitative interview data. At baseline, men will receive information (web or print) about weight loss and a pedometer. There will be no interim measurements or contacts by the research team. Men are therefore free to choose whether to try to lose weight or to self-monitor during the 12 months. They will not have access to the self-monitoring page on the study website until after the 12 month outcome assessment. The NIHR commissioning brief 14/185 asks for non-provision/usual practice. The control arm is as close as possible to "doing nothing", whilst remaining ethical (information, free choice to lose weight and later assistance via SMS to reduce disappointment bias). Men will be asked about their weight and any efforts they have made to change between enrolment and the 12 month assessment, and those choosing to receive alternative text messages will be followed up in person after 3 months using the same procedures as employed during the 3 months follow up of intervention participants.

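### The original-versus-alternative text comparison behind research question 3 uses non-randomised, differently selected groups, so a 3-month retention difference cannot be attributed to text style

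*Protocol*

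**What the plan says.** Main research question 3 (Protocol section 3) asks whether alternative texts are "more acceptable and likely to improve trial retention at 3 months than the existing text message intervention". Section 4.10 supplies the quantitative answer: stop requests, withdrawals and the proportion who "attend the 3 month assessments will be compared for the original and alternative text messages".

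The alternative-text group has two sources.

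- **Former controls.** Section 4.3, Control group: "At the 12 month outcome assessment men will be offered an alternative SMS intervention for 3 months". Taking the texts is a choice, and "those choosing to receive alternative text messages will be followed up in person after 3 months". Section 4.3, Intervention 1, adds that control men's web access stays limited "until they have provided outcome data at 12 months". Until the 12-month visit the research team makes no contact with them.
- **New recruits.** Lay summary: "Drop-outs from the control group at 12 months will be replaced through recruiting further men", until at least 30 men receive the alternative texts. Section 4.2 (vii) gives the target as 30 and 35 and explains the top-up by possible dropout and poor uptake. These men are not randomised. Their information sheet tells them beforehand that they will get texts only, with a 3-month assessment.

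The original texts go to men from randomisation, in both the SMS-only and the SMS-plus-incentive arms, throughout the year. In the incentive arm £50 is secured or lost at the 3-month weigh-in (section 4.3, Table 1).

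The protocol does not call the comparison non-randomised, does not plan to report the two sources separately, and does not say whether the original-text group includes the incentive arm.

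**The concern.** The outcome compared is staying in the study and attending. Former controls enter the alternative-text group only after doing that for a year and then opting in. The controls who would have been lost are replaced, so likely non-attenders leave the denominator. The original-text group keeps its early losses. Two text sets that engage men equally could then show different 3-month retention.

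Two smaller problems add to this. Section 4.10 ties only attendance to 3 months. Stop requests and withdrawals counted over the full period would cover 12 months for the original texts and 3 for the alternative ones. And if the incentive arm counts as original text, a cash incentive at the 3-month visit is mixed into the comparator.

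What is at stake is the answer to a numbered research question and, through it, the view taken of which style of text to carry into a full trial.

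**Working it through.** **Plan's own figures.** 3 × 35 = 105 randomised (section 4.9). The protocol gives no power, effect size or expected attendance for this comparison, so there is no further figure to reproduce.

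**Make-up of the alternative-text group.** The 12-month retention benchmark is 72% per group (section 3, progression criteria): 35 × 0.72 = 25.2, about 25 control completers. Opt-in is assumed at 100%, 80% or 60%.

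| Opt-in (assumed) | Former controls | New recruits to reach 30 | New recruits to reach 35 |
|---|---|---|---|
| 100% | 25 | 5 | 10 |
| 80% | 20 | 10 | 15 |
| 60% | 15 | 15 | 20 |

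Former controls are thus between 15/35 = 43% and 25/30 = 83% of the group.

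**Illustration A: two types of men, no text effect.** Let a1 and a0 be the 3-month attendance of men who would and would not complete 12 months. Assume new recruits attend like the original-text group, and opted-in former controls attend at a1.

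- Original: p = 0.72·a1 + 0.28·a0
- Alternative: q = [k·a1 + (T − k)·p] / T, with k former controls and T = 30 or 35
- Spurious gain: q − p = (k/T) × 0.28 × (a1 − a0), positive whenever a1 > a0

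Example with a1 = 95%, a0 = 50%: p = 0.684 + 0.140 = 0.824. With full opt-in and T = 30, q = (25 × 0.95 + 5 × 0.824)/30 = 0.929, a gain of 10.5 points. With 60% opt-in and T = 35, q = (15 × 0.95 + 20 × 0.824)/35 = 0.878, a gain of 5.4 points.

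| a1 / a0 (assumed) | Original | Spurious gain across opt-in and T |
|---|---|---|
| 90% / 80% | 87.2% | 1.2 to 2.3 points |
| 95% / 70% | 88.0% | 3.0 to 5.8 points |
| 95% / 50% | 82.4% | 5.4 to 10.5 points |
| 95% / 30% | 76.8% | 7.8 to 15.2 points |

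**Illustration B: original attendance fixed at 80%, former controls at 95–100%, new recruits at 80%.**

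- Full opt-in: (25 × 1.00 + 5 × 0.80)/30 = 0.967 down to (25 × 0.95 + 10 × 0.80)/35 = 0.907, a gain of 11 to 17 points.
- 60% opt-in: (15 × 1.00 + 15 × 0.80)/30 = 0.900 down to (15 × 0.95 + 20 × 0.80)/35 = 0.864, a gain of 6 to 10 points.

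The 17-point figure needs strong assumptions. If completers attend at 100% and the overall rate is 80%, the other 28% attend at (0.80 − 0.72)/0.28 = 29%.

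**What could offset it.** If the original-text group pools SMS-only with an equal-sized incentive arm whose attendance is higher by d, the comparator rises by d/2. Cancelling the 5.4 to 10.5 points of the 95%/50% case would need d of about 11 to 21 points. Former controls who disengaged during a year without contact would also attend below a1.

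**Precision.** At 82.4%, the 95% half-width of the difference is 1.96 × √[0.824 × 0.176 × (1/T + 1/n)]: 18.6 points for 30 against 35 men, 15.5 for 35 against 70.

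**The case against.** The strongest objections concern certainty and weight. No attendance or opt-in rate comes from the protocol, so any size is illustrative. The direction is not guaranteed either: the incentive arm and the year without contact both pull the other way. New recruits are not 12-month survivors and could be more than half the group. The study is mainly descriptive, this contrast is not a progression criterion, and no rule lets it choose the text version. Acceptability also rests on interviews and think-aloud work. Question 3 already refers to 3 months, and the counting window and the definition of the comparator could be settled in a statistical analysis plan.

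Most of this stands, and it limits severity. It does not remove the point. The protocol itself poses the comparative question, builds the group and names the contrast, without a caveat. Using the same follow-up procedures in both groups aligns measurement, not populations, and no later modelling choice makes these groups exchangeable.

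A reader might infer that the comparison is bound to make the alternative texts look better, or that the alternative group consists only of 12-month survivors. The protocol supports neither: the top-up dilutes survivor selection while adding a different selection, and the offsetting forces are real.

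**Conclusion.** The point holds at moderate severity. As written, the pooled contrast cannot answer question 3, because text style is confounded with how men entered each group. That conclusion rests on the protocol's text alone and needs no assumed rate.

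The bias probably favours the alternative texts, by roughly 1 to 17 points. That span assumes 72% completion, 60–100% opt-in, a target of 30 or 35, the attendance rates shown, and new recruits who attend like the original-text men. Its top end needs full opt-in and perfect attendance by former controls. The whole span is of the same order as, or smaller than, the sampling half-width of about 16 to 19 points. The data could therefore neither expose nor rule out the artefact.

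**What to change.** In section 4.10:

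1. Define the original-text comparator as the SMS-only arm, and show SMS plus incentive separately.
2. Count stop requests, withdrawals and attendance over the first 3 months of texts in every group.
3. Report former controls and new recruits separately, each descriptively with confidence intervals.
4. State that the comparison is non-randomised.

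In section 3, reword question 3 so that it asks for a description of acceptability and 3-month retention with the alternative texts and does not attribute a difference to text style.

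Two tempting substitutes should be avoided. The first is to rest question 3 on the new recruits alone. With 5 to 10 of them against 35 SMS-only men at an assumed 80%, the half-width is 1.96 × √[0.16 × (1/5 + 1/35)] = 37 points, or 28 points with 10. These men also agreed to a known text-only offer, not to three-arm randomisation. The second is to restrict SMS-only men to those who attended at 12 months. That conditions on something that happened after their texts, whereas former controls were selected before receiving theirs.

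The cost is wording only, with no new data. The downside is smaller groups and a weaker conclusion.
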